7.2.3 Dose Reductions

NKTR-102 doses for an individual patient may be reduced 25 mg/m² based on conditions listed in the **Table 3** below. Only 2 dose reductions are permitted. Subjects should be discontinued from the study treatment if toxicity requires a dose reduction beyond the 2 dose reduction steps. Dose re-escalation for NKTR-102 is not permitted.

Table 3. Dose Modifications Based on Toxicities

Toxicity NCI CTCAE Grade	During a Cycle: Recommended Guidelines for Management and Supportive Care	Day 1 of New Cycle: Dose Modifications Based on Worst Toxicity in Prior Cycle
Thrombocytopenia / Anemia / Neutropenia / Febrile Neutropenia		
Grade 1 or Grade 2	-	Maintain dose level

Grade 3
	
Platelets: consider platelet transfusion if active bleeding.
 
ANC: consider growth factor support in accordance with local guidelines.
 
Hgb: erythropoietin-stimulating agents or transfusion as appropriate.
 
If present on a treatment day, hold therapy for a week or until toxicity resolves to Hgb \geq 8 g/dL or 80 g/L; ANC \geq 1.5×10^9/L; platelets \geq 75×10^9/L, with a maximum of 28 days.
	
↓ 1 dose level after 1st occurrence. ↓ 1 dose level after 2nd occurrence. Discontinue patient after 3rd occurrence.

Grade 4
	
Platelets: consider platelet transfusion if platelets < 20K or with active bleeding.
 
ANC: consider growth factor support in accordance with local guidelines.
 
Antibiotic (Fluoroquinolones) should be initiated even in the absence of fever or diarrhea.
 
Hgb: consider erythropoietin-stimulating agents or transfusion as appropriate.
 
If present on a treatment day, hold therapy for a week or until toxicity resolves to Hgb \geq 8 g/dL or 80 g/L; ANC \geq 1.5×10^9/L; platelets \geq 75×10^9/L, with a maximum of 28 days.
	
↓ 1 dose level after 1st occurrence. ↓ 1 dose level after 2nd occurrence. Discontinue patient after 3rd occurrence.

Febrile Neutropenia
	
Subjects should be hospitalized immediately for IV antibiotic therapy if they develop neutropenic fever or sepsis (e.g., growth factor support; antibiotics); consider hospital admission.
	
↓ 1 dose level after 1st occurrence. ↓ 1 dose level after 2nd occurrence. Discontinue patient after 3rd occurrence.


Diarrhea Any Grade
	
Institute supportive care upon first loose stool. (Unless contraindicated, use loperamide). Monitor bowel function; if diarrhea continues with 1st supportive care agent, consider switching to a 2nd agent or add a 2nd agent (unless contraindicated, use diphenoxylate/atropine).
 
Monitor for dehydration, electrolyte abnormalities; correct if present.
 
Administer antibiotic therapy (oral fluoroquinolones) if the patient develops ileus, fevers or Grade 3/4 neutropenia.
 
Subjects should be immediately hospitalized for IV antibiotics therapy if they have evidence of colitis or ileus even in the absence of neutropenia or fever.
 
If worsening diarrhea, octreotide may be attempted.
 
Monitor bowel function for continued need of supportive care.
 
Stop supportive care after the patient is 48 hour without diarrhea.
	
Confirm with the patient that diarrhea is no longer present for ≥ 7 days without having received supportive care prior to retreatment.
 
Treatment may be delayed up to 28 days; after this, contact Medical Monitor.

Grade 1
	
If still present within 7 days prior to treatment hold therapy until diarrhea is no longer present for ≥ 7 days without having received supportive care.
	
Maintain dose level; consider prophylactic anti-diarrheal supportive care

Grade 2
	
If still present within 7 days prior to treatment hold therapy until diarrhea is no longer present for ≥ 7 days without having received supportive care.
	
↓ 1 dose level after 1st occurrence. ↓ 1 dose level after 2nd occurrence. Discontinue patient after 3rd occurrence.

Grade 3/4
	
If still present within 7 days prior to treatment hold therapy until diarrhea is no longer present for ≥ 7 days without having received supportive care.
	
↓ 2 dose level after 1st occurrence. Provided that adequate supportive care has been given to the patient, discontinue patient after 2nd occurrence. If the patient has not received adequate supportive care, retreatment may be attempted for a 2nd episode of Grade 3 diarrhea (re-instruct patient on supportive care). Patients must be discontinued for a 2nd episode of Grade 4 diarrhea.

Dehydration		
Grade 1 or Grade 2	Consider anti-emetic and/or anti-diarrheal therapy. If Grade 2 present on a treatment day, hold therapy for a week or until toxicity resolves to baseline or Grade \leq 1, with a maximum of 28 days.	Consider prophylactic anti-emetic therapy. Maintain dose level.
Grade 3	Use anti-emetic and/or anti-diarrheal therapy. If present on a treatment day, hold therapy for a week or until toxicity resolves to baseline or Grade \leq 1, with a maximum of 28 days.	Consider prophylactic anti-emetic therapy. \downarrow 1 dose level after 1st occurrence; \downarrow 1 dose level after 2nd occurrence Discontinue patient after 3rd occurrence
Grade 4	Use anti-emetic therapy and IV fluids. Consider hospital admission. If present on a treatment day, hold therapy for a week or until toxicity resolves to baseline or Grade \leq 1, with a maximum of 28 days.	Use prophylactic anti-emetic therapy. \downarrow 2 dose level after 1st occurrence. Discontinue patient after 2nd occurrence.
Nausea / Vomiting / Abdominal Pain		
Grade 1 or Grade 2	Consider anti-emetic therapy. If Grade 2 present on a treatment day, hold therapy for a week or until toxicity resolves to baseline or Grade \leq 1, with a maximum of 28 days.	Consider prophylactic anti-emetic therapy. Maintain dose level.
Grade 3 or Grade 4	Use anti-emetic therapy. Consider administration of IV fluids. If present on a treatment day, hold therapy for a week or until toxicity resolves to baseline or Grade \leq 1, with a maximum of 28 days.	After 1st occurrence use prophylactic anti-emetic therapy and maintain dose level \downarrow 1 dose level after 2nd occurrence Discontinue patient after 3rd occurrence
Other Drug-Related Non-Hematologic Toxicities (Except Fatigue/Asthenia and Alopecia)		
Grade 1 or Grade 2	Consider supportive care as appropriate. If Grade 2 present on a treatment day, hold therapy for a week or until toxicity resolves to baseline or Grade \leq 1, with a maximum of 28 days.	Maintain dose level (for Grade 2 toxicity, the Investigator may use discretion to \downarrow 1 dose level after 1 st occurrence depending on the nature of the toxicity).
Grade 3 or Grade 4	Use supportive care as appropriate. If present on a treatment day, hold therapy for a week or until toxicity resolves to baseline or Grade \leq 1, with a maximum of 28 days.	\downarrow 1 dose level after 1 st occurrence; supportive care as appropriate. \downarrow 1 dose level after 2 nd occurrence. Discontinue patient after 3 rd occurrence.

7.3 Concomitant Medication and Supportive Care

7.3.1 Anti-Emetic Therapy

Prophylactic anti-emetics will be allowed according to standard practices.

Based on investigator discretion, an investigator may prescribe prophylactic antiemetics prior to the first dose of the study drugs. The patient must be carefully monitored throughout the study period, and given adequate fluid and electrolyte replacement to prevent dehydration and electrolyte imbalance. Dexamethasone, ondansetron, lorazepam or prochlorperazine can be given at the discretion of the treating physician.

5. Patients who are dehydrated must promptly receive adequate IV fluids, electrolytes to combat electrolyte imbalance if present and antibiotics in case of fever. Serial complete and differential blood counts must be done for early identification of the concomitant occurrence of neutropenia.

7.3.3 Platelet Transfusion

Patients may receive transfusions (platelets or blood products) at the Investigator's discretion. If platelet count $< 20,000/\text{mm}^3$, 1 unit single-donor apheresis platelet transfusion may be given. A post-transfusion platelet count should be collected at 15 minutes post-transfusion to demonstrate increment.

7.3.4 Growth Factor Use

Prophylactic use of growth factor support is not permitted, however use of growth factor support in a setting of neutropenia is permitted. Use of growth factor support must follow American Society Clinical Oncology (ASCO), ESMO guidelines or standard of care at the local institution. If a patient required growth factor support during a previous cycle, a patient may be administered prophylactic growth factor support during a subsequent cycle at the investigator's discretion.

7.3.5 Other Antineoplastic Therapy

The administration of other antineoplastic therapy (e.g., chemotherapy, hormone therapy, immunotherapy, targeted therapy, monoclonal antibodies and radiation therapy) is not permitted. Patients requiring radiation therapy after the start of the study are considered as having progression of disease and must discontinue study treatment.

7.3.6 Bisphosphonates and Denosumab

Patients may continue or start Bisphosphonates and Denosumab if required during the study.

7.3.7 Medications NOT ALLOWED During Study (*P450 inhibitors/inducers*)

Because there is a potential for interaction of drug with other concomitantly administered drugs through the cytochrome P450 system, the electronic case report form (eCRF) must capture the concurrent use of all other drugs, over-the-counter medications, or alternative therapies. The Investigator should be alerted if the subject is taking any agent known to affect or with the potential to affect selected CYP450 isoenzymes.

In vitro drug interaction studies of NKTR-102 with cytochrome P450 3A4 enzyme (CYP3A4) have not been done. However, drug interactions have been documented between CYP3A4 enzymes and irinotecan and are listed in the Camptosar® USPI August 2010. Please refer to the Camptosar® package insert for further information.

St. John's Wort: St. John's Wort is an inducer of CYP3A4 enzymes. Exposure to the active metabolite SN-38 is reduced in patients receiving concomitant St. John's Wort. St. John's Wort should be discontinued at least 2 weeks prior to the first cycle of irinotecan, and St. John's Wort is contraindicated during irinotecan therapy.

Anticonvulsants: Exposure to irinotecan and its active metabolite SN-38 is substantially reduced in adult and pediatric patients concomitantly receiving the CYP3A4 enzyme-inducing anticonvulsants phenytoin, phenobarbital or carbamazepine. The appropriate starting dose for patients taking these anticonvulsants has not been formally defined. The following drugs are also CYP3A4 inducers: rifampin, rifabutin. For patients requiring anticonvulsant treatment, consideration should be given to substituting non-enzyme inducing anticonvulsants at least 2 weeks prior to initiation of NKTR-102 therapy. Dexamethasone does not appear to alter the pharmacokinetics of irinotecan.

Ketoconazole: Ketoconazole is a strong inhibitor of CYP3A4 enzymes. Patients receiving concomitant ketoconazole have increased exposure to irinotecan and its active metabolite SN-38. Patients should discontinue ketoconazole at least 1 week prior to starting irinotecan therapy and ketoconazole is contraindicated during irinotecan therapy.

Neuromuscular blocking agents: Interaction between irinotecan and neuromuscular blocking agents cannot be ruled out. Irinotecan has anticholinesterase activity, which may prolong the neuromuscular blocking effects of suxamethonium and the neuromuscular blockade of non-depolarizing drugs may be antagonized.

Atazanavir sulfate: Coadministration of atazanavir sulfate, a CYP3A4 and UGT1A1 inhibitor has the potential to increase systemic exposure to SN-38, the active metabolite of irinotecan.

The Principal Investigator should be contacted with any questions related to concomitant medications (from 4 weeks prior to the first dose of NKTR-102 through 4 weeks after the last dose of NKTR-102).

7.4 Duration of Treatment

Subjects may remain on study treatment in the absence of disease progression, unacceptable toxicity, and withdrawal from study or study termination. Patients who develop metastases in the central nervous system (CNS) as the only site of disease progression could receive therapeutic whole brain radiation therapy (WBRT), or gamma knife radiosurgery and after completion of WBRT continue on NKTR-102. Imaging studies are scheduled to be obtained after every other 21-day cycle.

7.5 Treatment Discontinuation

Upon treatment discontinuation all end of treatment evaluations and tests will be conducted. All subjects who discontinue due to an AE must be followed until the event resolves or stabilizes. Appropriate medical care should be provided until signs and symptoms have abated, stabilized, or until abnormal laboratory findings have returned to acceptable or pre-study limits. The final status of the AE will be reported in the subject's medical records and the appropriate eCRF.

Reasons for treatment discontinuation should be classified as follows:

- Death
- Progressive disease
- Treatment-related toxicity

- Toxicity unrelated to treatment
- Noncompliance
- Investigator judgment
 - The Investigator may withdraw a subject if, in his/her judgment, it is in the subject's best interest to do so.
- Subject voluntary withdrawal
 - A subject may withdraw from the study at any time, for any reason. If a subject discontinues treatment, an attempt should be made to obtain information regarding the reason for withdrawal.

Subjects who are unavailable for follow-up evaluations should be classified as lost to follow-up for 1 of the following reasons:

- Lost to follow-up: For a subject to be considered lost to follow-up, the investigator must make 2 attempts to re-establish contact with the subject. The attempts to re-establish subject contact must be documented (e.g., certified letter).
- Death: Date and cause of death will be recorded for those subjects who die within 30 days after last dose of study drug (telephone contact is acceptable).

7.6 Compliance

On Day 1 of each treatment cycle, study-treatment administration will be documented on the eCRF. Any deviations from the protocol-specified study drug administration will be documented, including the date and reason for each dosing noncompliance.

7.7 Subject Randomization and Registration

This is a non-randomized study. Patients will be categorized into two groups depending on their prior response to treatment. Group A (chemoresistant group) includes patients progressing < 3 months after first-line therapy and Group B (chemosensitive group) includes patients progressing \geq 3 months after first-line therapy.

7.8 Baseline Evaluations

The following will be performed \leq 14 days prior to initiation study drug:

- Informed consent: Must be completed prior to receiving any study-related procedures.
- Medical history (Full history)
- Physical examination, including vital signs, body weight, and height
- ECOG performance status
- Adverse events evaluation

- Tumor assessment by CT/PET or CT scan should be performed within 28 days prior to initiation of study drug
- CT scan/MRI brain (brain imaging is required in symptomatic patients to rule out brain metastases, but not required in asymptomatic patients)
- Pregnancy test (urine or serum) in females of childbearing potential. Must be done ≤ 7 days prior to initiation of study drug.
- Coagulation (INR, PTT)
- Hematology (4 hour fasting) (i.e., complete blood count (CBC) with automated differentials or the physician discretion; WBC, RBC, HGB, HCT, platelet, MCV, MCH, MCHC, %neutrophils, absolute neutrophils, %lymphocytes, absolute lymphocytes, %monocytes, absolute monocytes, %eosinophils, absolute eosinophils, %basophils, absolute basophils, %Large Unspecified Cells (LUC), %lymphocyte total, absolute lymphocyte total, platelet confirmation, and differential confirmation)
- Chemistry (4 hour fasting) (i.e., complete metabolic panel (CMP): chloride, CO₂, potassium, sodium, BUN, glucose, calcium, creatinine, total protein, albumin, total bilirubin, alkaline phosphatase, AST, ALT, A/G ratio, BUN/creatinine ratio, osmol (Calc), anion gap)
- 12-Lead ECG. The patient will be asked to lie down and rest for about 10 minutes before this procedure.

7.9 Evaluations Performed on Cycle 1 Day 1

- Medical history (Updated from previous clinical visit)
- Physical examination, including vital signs and body weight
- ECOG performance status
- Adverse events evaluation
- Hematology (4 hour fasting) (i.e., complete blood count (CBC) with automated differentials or the physician discretion; WBC, RBC, HGB, HCT, platelet, MCV, MCH, MCHC, %neutrophils, absolute neutrophils, %lymphocytes, absolute lymphocytes, %monocytes, absolute monocytes, %eosinophils, absolute eosinophils, %basophils, absolute basophils, %Large Unspecified Cells (LUC), %lymphocyte total, absolute lymphocyte total, platelet confirmation, and differential confirmation)
- Chemistry (4 hour fasting) (i.e., complete metabolic panel (CMP): chloride, CO₂, potassium, sodium, BUN, glucose, calcium, creatinine, total protein, albumin, total bilirubin, alkaline phosphatase, AST, ALT, A/G ratio, BUN/creatinine ratio, osmol (Calc), anion gap)
- Pharmacogenetic blood sample

7.10 Evaluations Performed Weekly for Cycle 1

- Medical history (Updated from previous clinical visit)
- Physical examination, including vital signs and body weight
- ECOG performance status
- Adverse events evaluation
- Hematology (4 hour fasting) (i.e., complete blood count (CBC) with automated differentials or the physician discretion; WBC, RBC, HGB, HCT, platelet, MCV, MCH, MCHC, %neutrophils, absolute neutrophils, %lymphocytes, absolute lymphocytes, %monocytes, absolute monocytes, %eosinophils, absolute eosinophils, %basophils, absolute basophils, % Large Unspecified Cells (LUC), %lymphocyte total, absolute lymphocyte total, platelet confirmation, and differential confirmation)
- Chemistry (4 hour fasting) (i.e., complete metabolic panel (CMP): chloride, CO₂, potassium, sodium, BUN, glucose, calcium, creatinine, total protein, albumin, total bilirubin, alkaline phosphatase, AST, ALT, A/G ratio, BUN/creatinine ratio, osmol (Calc), anion gap)

7.11 Evaluations Performed Prior to Treatment on Day 1 of Subsequent Cycles

- Medical history (Updated from previous clinical visit)
- Physical examination, including vital signs and body weight
- ECOG performance status
- Adverse events evaluation
- Hematology (4 hour fasting) (i.e., complete blood count (CBC) with automated differentials or the physician discretion; WBC, RBC, HGB, HCT, platelet, MCV, MCH, MCHC, %neutrophils, absolute neutrophils, %lymphocytes, absolute lymphocytes, %monocytes, absolute monocytes, %eosinophils, absolute eosinophils, %basophils, absolute basophils, %Large Unspecified Cells (LUC), %lymphocyte total, absolute lymphocyte total, platelet confirmation, and differential confirmation)
- Chemistry (4 hour fasting) (i.e., complete metabolic panel (CMP): chloride, CO₂, potassium, sodium, BUN, glucose, calcium, creatinine, total protein, albumin, total bilirubin, alkaline phosphatase, AST, ALT, A/G ratio, BUN/creatinine ratio, osmol (Calc), anion gap)
- 12-Lead ECG (prior to Cycle 2 and Cycle 3, if clinically indicated). The patient will be asked to lie down and rest for about 10 minutes before this procedure.
- Radiological assessments (same method as baseline) to be performed every other cycle after completing Cycle 2. Confirmation of objective tumor responses should be performed consistent with RECIST 1.1.

7.12 Evaluations Performed at 30 Day Follow-Up

- Medical history (Updated from previous clinical visit)
- Physical examination, including vital signs and body weight
- ECOG performance status
- Adverse events evaluation
- Hematology (4 hour fasting) (i.e., complete blood count (CBC) with automated differentials or the physician discretion; WBC, RBC, HGB, HCT, platelet, MCV, MCH, MCHC, %neutrophils, absolute neutrophils, %lymphocytes, absolute lymphocytes, %monocytes, absolute monocytes, %eosinophils, absolute eosinophils, %basophils, absolute basophils, %Large Unspecified Cells (LUC), %lymphocyte total, absolute lymphocyte total, platelet confirmation, and differential confirmation)
- Chemistry (4 hour fasting) (i.e., complete metabolic panel (CMP): chloride, CO₂, potassium, sodium, BUN, glucose, calcium, creatinine, total protein, albumin, total bilirubin, alkaline phosphatase, AST, ALT, A/G ratio, BUN/creatinine ratio, osmol (Calc), anion gap)

7.13 Survival Follow-up

- Patients will also be followed for survival every 3 months following the 30 day follow-up visit. Survival follow-up assessments may be collected via telephone.

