Objectives	
Primary Objective:
 
 To evaluate the 18-week progression free survival (PFS) rate of relapsed SCLC patients treated with NKTR-102. 
Secondary Objectives:
 
 To evaluate the objective response rate. To evaluate the duration of response. To evaluate the overall survival. To evaluate the toxicity of NKTR-102 in this patient population. 
Correlative Objective:
 
 To explore the correlation between UGT1A1 polymorphisms and NKTR-102 toxicities.
Study Design	This is a single stage Phase II study of relapsed small cell lung cancer patients who have received only one prior systemic therapy regimen. There will be 2 patient cohorts: those progressing on first-line therapy < 3 months after completion of treatment (Group A: chemo resistant) and those progressing on first-line therapy ≥ 3 months after completion of treatment (Group B: chemo sensitive). Etirinotecan pegol will be administered at 145 mg/m ² IV once every 3 weeks. Cycles will be repeated every 21 days (± 3 days) until disease progression. Patients who develop metastases in the central nervous system (CNS) as the only site of disease progression could receive therapeutic whole brain radiation therapy (WBRT), or gamma knife radiosurgery and after completion of WBRT continue on NKTR-102. Imaging studies are scheduled to be obtained after every other 21-day cycle.
Target Accrual and Study Duration	This study will accrue a total of 38 patients over approximately 3 years (Group A; 20 patients, Group B; 18 patients). Patients will be on study for approximately 18 – 24 months.
Study Procedures	
Adverse Events: From time of Cycle 1 Day 1 until 30 days after receiving last dose of study drug.
 
Hematology: ≤ 14 days prior to initiation of study drug, Cycle 1 (Day 1 and weekly), and prior to treatment on Day 1 of subsequent cycles, 30-Day Follow-Up.
 
Chemistry: ≤ 14 days prior to initiation of study drug, Cycle 1 (Day 1 and weekly), prior to treatment on Day 1 of subsequent cycles, 30-Day Follow-Up.
 
Physical Examination (including vital signs, body weight, and height):

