3.2 Secondary Objectives

- To evaluate the objective response rate.
- To evaluate the duration of response.
- To evaluate the overall survival.
- To evaluate the toxicity of NKTR-102 in this patient population.

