7 TREATMENT PLAN

7.1 Dosage and Administration

NKTR-102 will be administered 145 mg/m² IV dose over a 90-minute period once every 3 weeks. Cycles will be repeated every 21 days (\pm 3 days). The patient's actual weight at baseline (Day 1 of Cycle 1) will be used. It is not necessary to correct dosing based on ideal body weight. If the patient's weight changes by > 10% during the course of the study, the body surface area and drug doses should be recalculated.

Treatment will be administered in an outpatient basis. Reported adverse events (AEs) and potential risks are described in Investigator's Brochure. Appropriate dose modifications are described in **Section 7.2**. No other investigational or commercial drugs or therapies other than those described below may be administered with the intent to treat the subject.

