- 7 Tumor assessment must be performed at least every other cycle after completing Cycle 2. Tumor assessment may be performed ± 3 days prior to treatment on Day 1 of subsequent cycles. Tumor assessment should be performed at any time during the treatment cycle that disease progression is clinically suspected so that patient can go off treatment and receive other therapy. If PET-CT was used at baseline, CT only may be used for subsequent cycles.
- 8 Brain imaging is required in symptomatic patients to rule out brain metastases, but is not required in asymptomatic patients.
- 9 Women of childbearing potential only. Must be done ≤ 7 days prior to initiation of study drug.
- 10 Hematology (i.e., complete blood count (CBC) with automated differentials or the physician discretion; WBC, RBC, HGB, HCT, platelet, MCV, MCH, MCHC, %neutrophils, absolute neutrophils, %lymphocytes, absolute lymphocytes, %monocytes, absolute monocytes, %eosinophils, absolute eosinophils, %basophils, absolute basophils, %Large Unspecified Cells (LUC), %lymphocyte total, absolute lymphocyte total, platelet confirmation, and differential confirmation).
- 11 Chemistry (i.e., complete metabolic panel (CMP): chloride, CO₂, potassium, sodium, BUN, glucose, calcium, creatinine, total protein, albumin, total bilirubin, alkaline phosphatase, AST, ALT, A/G ratio, BUN/creatinine ratio, osmol (Calc), anion gap).
- 12 Pharmacogenetic blood sample collection will be obtained at Day 1 of Cycle 1.
- 13 The patient will be asked to lie down and rest for about 10 minutes before this procedure.
- 14 Prior to Cycle 2 and Cycle 3, if clinically indicated.
- 15 Survival follow-up assessments may be collected via telephone.

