11 STATISTICAL METHODOLOGY

11.1 Sample Size Determination and Analysis

In a Phase II and Phase III study of single agent topotecan or single agent irinotecan as shown in **Table 1** in recurrent SCLC, the median time to progression of the arms were 2.2 - 4 months.^{6,8-12} Based on this, the primary endpoint of this trial will be the proportion of patients who are progression-free at 18 weeks. Progression-free survival was chosen as the primary endpoint, rather than response rate, as this is appropriate clinical endpoint for cytotoxic agents such as NKTR-102 and for SCLC. A single-stage design will be used to assess the primary endpoint for each patient group. A treatment success was defined as a patient who was progression-free at 18 weeks. To evaluate Group A, the largest success proportion where the proposed treatment regimen would be considered ineffective in this population is 5%, and the smallest that would warrant further subsequent studies is 25%. Twenty evaluable patients will be entered on this study. If 2 or fewer successes are observed, this regimen will be considered ineffective in this patient population. If 3 or more successes are observed, this will be considered evidence that this treatment may be recommended for further testing in subsequent studies. Assuming that the

number of successes is binomially distributed, this design controls the Type I Error to be $< 10\%$ and has 90% power to detect 25% 18-week PFS rate. To evaluate Group B, the largest success proportion where the proposed treatment regimen would be considered ineffective in this population is 10%, and the smallest that would warrant further subsequent studies is 35%. Eighteen evaluable patients will be entered on this study. If 3 or fewer successes are observed, this regimen will be considered ineffective in this patient population. If 4 or more successes are observed, this will be considered evidence that this treatment may be recommended for further testing in subsequent studies. Assuming that the number of successes is binomially distributed, this design controls the Type I Error to be $< 10\%$ and has 90% power to detect 25% 18-week PFS rate. Patients who come off study (e.g., due to toxicity) and start an off-protocol therapy prior to 18 weeks will be considered failures at that point.

The evaluable population is defined as patients who meet eligibility requirements and receive any protocol treatment. Unevaluable patients will be replaced.

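### No contact scheduled after the 30-day visit collects subsequent therapy or progression, so some week-18 failures among patients who stop early without progression may go unrecorded

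*Combined protocol and SAP*

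**What the plan says.** Section 11.1 sets the endpoint: "A treatment success was defined as a patient who was progression-free at 18 weeks". It adds that patients who leave the study, with toxicity as the example, and "start an off-protocol therapy prior to 18 weeks will be considered failures at that point". Every eligible, treated patient enters the primary analysis, so a patient who stops early stays in the denominator.

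The collection schedule is as follows.

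- **On treatment.** Scans are tied to cycles. Table 4, footnote 7: "Tumor assessment must be performed at least every other cycle after completing Cycle 2". The tumor assessment row is marked only at screening and before Day 1 of later cycles.
- **30-day visit (section 7.12).** History, examination, performance status, adverse events and laboratory tests. There is no tumor assessment.
- **Afterwards (section 7.13).** "Patients will also be followed for survival every 3 months following the 30 day follow-up visit". Table 4, footnote 15: "Survival follow-up assessments may be collected via telephone". The last column of Table 4 contains the survival row and nothing else.

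Section 11.1 gives one censoring rule for both PFS and survival: the date the patient was last known to be alive. It has no rule for a patient whose progression status at week 18 is unknown.

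**The concern.** To apply the failure rule, the analyst must know, for every patient who stopped without progression, whether other therapy or progression came before week 18. After the 30-day visit no scheduled item supplies either date. For a patient who stops early, that visit can fall weeks before the endpoint.

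In the Kaplan-Meier analysis the consequence follows from the text. A report after week 18 that the patient is alive moves the censoring date past week 18, although disease status was last looked at much earlier. In the binomial count it is a possibility: the plan does not say how unknown status is scored, and the same patient could be entered as a success. The error runs in one direction, towards the drug. The decision thresholds are 3 of 20 and 4 of 18, so very few misclassified patients matter.

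**Working it through.** **1. The plan's own operating characteristics** (section 11.1; exact binomial)

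- Group A, n = 20, success if at least 3: P(X ≥ 3 | 20, 0.05) = 0.0755; P(X ≥ 3 | 20, 0.25) = 0.9087. This reproduces the stated type I error below 10% and power of 90%.
- Group B, n = 18, success if at least 4: P(X ≥ 4 | 18, 0.10) = 0.0982; P(X ≥ 4 | 18, 0.35) = 0.9217. The type I error statement holds. (The Group B text prints its power against 25%, where the rule gives 0.694. That is a separate matter and is not used here.)

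**2. Where the 30-day visit falls**

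Inputs: section 7.1, "Cycles will be repeated every 21 days"; the visit is taken as 30 days after the last dose, in line with the synopsis adverse event window, "until 30 days after receiving last dose of study drug"; week 18 = 18 × 7 = day 126. With first dose as day 0, the last dose in cycle c is on day 21(c − 1), the visit is on day 21(c − 1) + 30, and the gap is 126 minus the visit day. The first survival contact is put 91 days after the visit.

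| Last dose in cycle | Visit day | Gap to day 126 | First survival contact |
|---|---|---|---|
| 1 | 30 | 96 | 121 |
| 2 | 51 | 75 | 142 |
| 3 | 72 | 54 | 163 |
| 4 | 93 | 33 | 184 |
| 5 | 114 | 12 | 205 |
| 6 | 135 | −9 | 226 |

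Calling the first dose day 1 shortens each gap by one day. Only after a Cycle 1 stop does a survival contact fall before week 18, and Table 4 lists only survival for it.

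**3. How firm the Cycle 5 boundary is**

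- Visit window of ±7 days (Table 4): Cycle 5 visit on days 107 to 121, Cycle 6 visit on days 128 to 142.
- Cycle windows of ±3 days accumulated: Cycle 5 visit on days 102 to 126, Cycle 6 visit on days 120 to 150.
- Time origin: the synopsis counts 18 weeks from drug, while section 11.1 counts PFS from registration. The lag is not stated. If it were 12 to 14 days (assumed), week 18 would fall 114 to 112 days after first dose. The Cycle 5 gap becomes 0 to −2 days, and the Cycle 4 gap 21 to 19 days.

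Cycles 1 to 4 are therefore exposed under either origin. Cycle 5 is exposed only if time runs from first dose on the nominal schedule.

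**4. Effect on the decision rule**

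The documents give no misclassification rate, so a range is assumed. If a fraction q of true failures is scored as success, the apparent null rate is p₀ + (1 − p₀)q.

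| q | Group A null rate | Group A type I error | Group B null rate | Group B type I error |
|---|---|---|---|---|
| 0 | 0.050 | 0.0755 | 0.100 | 0.0982 |
| 2% | 0.069 | 0.1561 | 0.118 | 0.1548 |
| 5% | 0.0975 | 0.3088 | 0.145 | 0.2587 |

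Expected misclassified patients at q = 2% and 5%: Group A, 20 × 0.95 × q = 0.38 and 0.95; Group B, 18 × 0.90 × q = 0.32 and 0.81.

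As a conditional marker, if exactly one patient is scored a success regardless of outcome: P(X ≥ 2 | 19, 0.05) = 0.2453 in Group A and P(X ≥ 3 | 17, 0.10) = 0.2382 in Group B.

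**The case against.** A reader might infer that all failures after the 30-day visit are lost. The documents do not support that. Deaths are captured by survival follow-up. Patients stopped for progression are already failures. A need for radiation is treated as progression (section 7.3.5). Symptomatic deterioration is reported as progression, with later efforts to document it objectively (section 8.4). Patients who stop for an adverse event are followed until it resolves or stabilizes (section 7.5), and follow-up of related serious events may run to the start of a new treatment (section 9.3.1). Toxicity stops are thus better followed than other stops. All this stands. What remains is the patient who stops without progression and then progresses or starts other therapy in the gap, with no open event to bring it to light.

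Nor do the documents say that the survival call asks only about vital status. No call script or case report form is shown. What can be said is that nothing more is scheduled.

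Nor do they say that unknown status counts as success. It can equally be argued that an unassessed patient has not been shown to be progression-free. That is fair, but the plan does not say so, and its censoring rule points the other way.

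Few patients may reach the gap. If progression were exponential (an assumption), the nulls imply 0.05^(6/18) = 37% progression-free at week 6 and 0.05^(12/18) = 14% at week 12 in Group A, and 46% and 22% in Group B. Only some of these would stop without progression and then fail unseen. This is why the 24.5% and 23.8% figures should not be read as the trial's type I error: they force one success with certainty.

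Finally, one secondary objective is "To evaluate the duration of response", and a reader might conclude that responders who stop early have no end date. They can be censored at their last assessment, so that stronger claim fails.

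**Conclusion.** The point holds in limited form. The plan has a failure rule whose input is not scheduled to be collected for patients who stop without progression after Cycles 1 to 4 (Cycle 5 conditionally). Its censoring rule can then carry them past week 18 as event-free. The exposed period runs from 33 days (Cycle 4) to 96 days (Cycle 1) on the nominal schedule from first dose.

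The number of patients affected is not in the documents. Section 1.3.2 makes early toxicity stops plausible: it reports Grade 3 diarrhea in 23% of the breast cancer study at the recommended dose and schedule, and a median onset of 93 days (range 8 to 107) on the 21-day schedule. It does not say how many such patients stop treatment.

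Under the assumed 2% to 5% misclassification, type I error is 15.6% to 30.9% in Group A and 15.5% to 25.9% in Group B, against the stated limit of 10%. These rates correspond to fewer than one expected patient per group. This is a risk to the primary result that is cheap to remove, not a demonstrated bias.

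**What to change.** **Section 7.13 and Table 4.** Add to each survival contact the date and type of first subsequent anticancer therapy, and the date of any known progression. Add one telephone contact at week 18 for patients who stopped without progression.

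**Section 11.1, success count.** A call cannot establish progression-free status by RECIST. State therefore that a patient without documented progression-free status at week 18 counts as not a success and stays in the denominator.

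**Section 11.1, Kaplan-Meier analysis.** Separate the two censoring rules. Censor PFS at the last tumor assessment, and keep the date last known alive for overall survival.

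**Cost.** Two form fields and one call for a few patients, with no added scan or clinic visit. The price is a slightly conservative success count, since a patient who was truly progression-free but not documented as such would be scored as not a success.
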